5.3 Subject withdrawal

Participants that are randomized but do not receive study drug/placebo before 1 year of life will be withdrawn from the study.

5.4 Recruitment/enrollment procedures protocol

Expected duration of accrual of subjects is approximately 48 months. Recruitment will be conducted using standard procedures. To help with recruitment, information describing the study will be developed for print, electronic, and social media. Subjects' parent/guardian will be approached for participation, either in person or by telephone, by site study coordinators or investigators, who will obtain parental consent following standard procedures. The specific procedures will be in compliance with the requirements of each site's Institutional Review Board.

6 STUDY PROCEDURES

6.1 Preoperative Assessment – Screening Procedures and Baseline

Measurements

- 1. Obtain a signed and dated Informed Consent Form (ICF) prior to any study related procedures.
- 2. Enter all demographic, preoperative risk factor and past medical/surgical history data into the STS-CHSD as per routine
- 3. Obtain a unique subject ID from the IBM Clinical Development database. This subject ID will also serve as a unique patient identifier allowing cross-linking across databases. It must also be entered into the site's surgical database under the study identifier tab as the "STS-related clinical trial ID" (see section 6.4). In addition the STS "Operation ID" must be entered into both databases and will serve as a double check in the event that the IBM Clinical Development subject ID is incorrectly entered into either of the 2 databases.
- 4. Perform routine preoperative assessment

6.2 Baseline/Pre-Dose Assessment

After the parent or legally authorized representative has signed the IRB-approved informed consent form, and after it has been determined that the patient satisfies all inclusion and exclusion criteria, the following evaluations will be performed and entered directly into the study database (STS-CHSD):

1. Baseline demographics (race, gender, date of birth, age, weight, age and weight at surgery)

Version 6.0

- 2. Fundamental cardiac diagnosis as defined by the STS-CHSD
- 3. Presence of any of the 41 STS-CHSD defined preoperative risk factors including mechanical ventilation to treat cardiorespiratory failure, sepsis, stroke, renal failure or hepatic dysfunction as defined by the STS-CHSD.
- 4. Presence of any non-cardiac anatomic abnormality, genetic syndrome or chromosomal anomaly as defined by the STS-CHSD.

6.3 Study Procedures During Study Drug Administration

The following procedures or evaluations will be performed during and immediately following the drug administration and the data recorded as indicated:

- 1. Record study drug/placebo dosing information including dose and timing of drug administration into the IBM Clinical Development database.
- 2. Immediately (within 1 business day of first becoming aware of the adverse event) enter all serious, study drug-related adverse events into the IBM Clinical Development database.

6.4 Study Procedures After Study Drug Administration During Hospitalization

The following information will be collected using the standard STS-CHSD data collection forms consistent with usual institutional practice:

- 1. Record all post-operative complications using standard STS-CHSD data element definitions (see section 11.2 for definitions)
- 2. Record all subsequent surgeries (CPB or non-CPB cardiovascular or non-cardiovascular)
- 3. Record duration of mechanical ventilation
- 4. Record post-operative hospital length of stay
- 5. Record operative mortality (in-hospital death or death after hospital discharge but within 30 days of the surgery/administration of study drug/placebo)

All other aspects of care, including administration of clinically indicated medications can be provided per routine standard of care.

Serious, study drug-related adverse events may require expedited reporting and must be submitted into the IBM Clinical Development database. Sites must report these events within 1 business day of first becoming aware of the event.

The variables listed in Table 4 are not collected by the STS-CHSD and will need to be collected directly from the Electronic Health Record. These variables must be entered directly into the relevant databases as specified in Table 4.

Variable	Definition	Database
Post-operative highest blood	Enter the highest post-operative blood glucose within 72hrs of	IBM Clinical
glucose	surgery	Development
Post-operative insulin	Was insulin administered within 24 hours of surgery?	IBM Clinical
administration		Development
Post-operative adrenal suppression	Was hydrocortisone administered within 72 hours of surgery?	IBM Clinical
		Development
Preoperative creatinine	Enter the last serum creatinine level obtained prior to surgery	IBM Clinical
-		Development

Table 4: Additional variables to be captured from the electronic health record

Highest post-operative creatinine	Enter the highest serum creatinine within 72 hours of surgery	IBM Clinical
		Development
Lowest post-operative potassium	Enter the lowest post-operative potassium within 72 hours of	IBM Clinical
	surgery	Development
Highest post-operative AST	Enter the highest AST within 72 hours of surgery	IBM Clinical
		Development
Highest post-operative ALT	Enter the highest ALT within 72 hours of surgery	IBM Clinical
		Development
Highest post-operative lactate	Enter the highest lactate within 72 hours of surgery	IBM Clinical
		Development
Lowest post-operative serum	Enter the lowest serum cortisol level obtained within 72hrs of	IBM Clinical
cortisol	surgery	Development

6.5 PK/PD/Biomarker sampling procedures (select sites)

A limited PK/PD/Biomarker sampling scheme will be employed such that no more than 5600 μ l (7 samples, 800 μ l per sample) of blood is obtained (Table 5). Blood samples will be collected in 800 μ L aliquots. Children who have only 1 evaluable PK sample will be included in the analysis, but additional participants may be enrolled to ensure at least 100 children with < 4 adequate PK samples.

Table 5. PK/PD/Biomarker samplin

Sample Number	Per Patient Prioritization	Time	Per patient blood collection
1	Please always try to collect this	Pre-dose (biomarker only)	$4 \ge 200 \text{ uL} = 800 \text{ uL}$
2		0-30 minutes after the start of CPB	
3	Collect a minimum of 2 of any	0-30 minutes after MUF	
4	of these 5 time points to collect	1-2 hours after completion of CPB	4 x 200 uL = 800 uL
5	a minimum total of 3 time	4-6 hours after completion of CPB	$4 \ge 200 \text{ uL} = 800 \text{ uL}$
6	points per participant.	16-24 hours after completion of CPB	
7	If participating in the biomarker arm, then please always try to collect this	36-48 hours after completion of CPB	4x 200 uL = 800 uL

Timed PK/PD/Biomarker sample handling procedures (plasma):

Assays to measure methylprednisolone concentrations and measures of the inflammatory response to CPB in plasma will be conducted at a central lab using validated bioanalytical assays. The date and time will be recorded for the administration of study drug/placebo, and the acquisition time of the PK sample.

7 TREATMENTS TO BE ADMINISTERED

7.1 Description of Study Treatments

Eligible subjects will be randomized prior to their electively scheduled surgery in a 1:1 fashion to methylprednisolone (30mg/kg) versus placebo as summarized in table 2 above. The dosages for administration (30 mg/kg) are based upon expert consensus regarding current practice and a previous dosing study. Intravenous methylprednisolone is available in a **preservative free** single use "Act-O-Vial Page 14 of 96

System" containing powder (40mg, 125mg, 500mg and 1000mg options are available) and diluent. Study drug will be provided "off the shelf" by study sites and prepared following local pharmacy protocols. Only preservative-free solutions will be used for this trial due to safety concerns with the administration of benzyl alcohol preservatives in infants. Study drug will be mixed with isotonic saline in a syringe to create a solution. Placebo preparations will consist of isotonic saline only and will be prepared in identical syringes so as to be physically indistinguishable from study drug.

7.2 Route of Administration

For the purposes of this trial methylprednisolone will be administered as a bolus dose administered directly into the CPB priming solution (intraoperative administration).

7.3 Storage and Administration

Study drug/placebo will be prepared by the site investigational pharmacy and delivered to the operating room from the investigational pharmacy on the day of study drug/placebo administration. All co-investigators, staff administering study drug/placebo and other care providers will be blinded to study drug/placebo allocation. Start and stop times of study drug administration must be documented by the investigational pharmacy in the IBM Clinical Development database.

8 STUDY DRUG ACCOUNTABILITY

8.1 Medications/Treatments Permitted and Not Permitted during the Study

8.1.1 Rescue Medication, Emergency Procedures and Additional Treatments(s)

Management would be symptomatic treatment (e.g., severe hypertension) or observation and monitoring (e.g., mild hyperglycemia).

8.1.2 Restrictions regarding concomitant treatment

Subjects may be treated with other medications at the discretion of their physicians.

8.2 Emergency Unblinding

An emergency code break can be requested from the site research pharmacist after full discussion with the STRESS PI. This code break may be used in rare life-threatening or emergency situations when the identity of the study drug must be known to the investigator in order to provide appropriate medical treatment or if required to assure safety of trial participants. If the code break for a subject is required, the DCC must be informed within one working day of the event. The reason for breaking the code will be documented by the Data Coordinating Center (Duke Clinical Research Institute) accordingly.

9 SAFETY ASSESSMENTS AND MONITORING

9.1 Collection and Reporting

Due to the unique study design, adverse events will be recorded by the site as complications and/or other adverse event data variables specifically captured by the site's surgical database using STS-CHSD data element definitions (see Section 11.2).

Serious, study drug-related adverse events will be reported by site investigators or qualified designee from the time of study drug administration through 7 days after study drug administration on the SAE eCRF in the IBM Clinical Development database within 1 business day of first becoming aware of the event. The site investigator's reported relationship assessment to study drug will be confirmed or assessed otherwise by a Safety Medical Monitor at the Duke Clinical Research Institute.

9.2 Definitions of Adverse Events (AEs), Suspected Adverse Reaction and

Serious Adverse Events

The FDA Final Rule on IND Safety Reporting Requirements [http://edocket.access.gpo.gov/2010/pdf/2010-24296.pdf] provides the following definitions:

Adverse events (AEs) An AE is any untoward medical occurrence associated with the use of a drug in a subject whether or not considered drug- or biologic-related. An AE can therefore be any unfavorable and unintended sign, symptom, or disease temporally associated with the use of a pharmaceutical product or biologic.

A **suspected adverse reaction (SAR)** is any adverse event for which there is a reasonable possibility that the drug caused the adverse event. A "reasonable possibility" suggests there is a causal relationship between the drug and the adverse event. "Suspected adverse reaction" implies a lesser degree of certainty about causality than adverse reaction, which means any adverse event caused by a drug.

Serious adverse events: An adverse event or suspected adverse reaction is considered serious if, in the view of either the site investigator or the IND sponsor, it results in any of the following outcomes:

- 1. Death
- 2. Life-threatening AE: Places the subject at immediate risk of death at the time of the event as it occurred. It does not include an AE that, had it occurred in a more severe form, might have caused death.
- 3. Persistent or significant incapacity or substantial disruption of the ability to conduct normal life functions
- 4. Inpatient hospitalization or prolongation of existing hospitalization

An important medical event that may not result in death, be life threatening, or require hospitalization may be considered a serious adverse event when, based upon appropriate medical judgment, it may jeopardize the subject and may require medical or surgical intervention to prevent one of the outcomes listed in the definition above. This determination is based on the opinion of either the investigator or sponsor (e.g., if either believes it is serious, it must be considered serious).

Laboratory abnormalities are not specifically captured by institutions as part of their STS-CHSD and will not be considered AEs unless they result in a post-operative complication that sites report to the STS-CHSD. In this case, the clinical diagnosis rather than the laboratory term will be used by the reporting investigator (e.g., renal failure versus elevated creatinine).

9.3 Assessment of Severity

The determination of severity rests on medical judgment of a medically qualified investigator. For adverse events captured by the site's surgical database, the data monitoring committee will review these events every 6-months following transfer of data to the data coordinating center at the Duke Clinical Research Institute. For suspected unexpected serious adverse reactions, monitoring will be performed continuously and event severity will be graded by the study sponsor. The severity of suspected adverse reactions and study drug related SAEs will be graded using the following definitions:

1. MILD: Participant is aware of symptoms or has minor findings but tolerates them well and no or minimal intervention required.

2. MODERATE: Participant experiences discomfort enough to cause interference with usual activity and may warrant intervention.

3. SEVERE: Participant experiences symptoms that are incapacitating with inability to do usual activities or that significantly affect clinical status and warrant intervention.

Study personnel will enter the study drug-related serious adverse event data into the IBM Clinical Development database. The STRESS Trial PI / IND sponsor will be responsible for adjudicating severity and relatedness of these events and determining which events should be reported in expedited fashion to FDA. The IND sponsor or designee will submit expedited safety reports (IND Safety Reports) to the FDA and other regulatory agencies as necessary, and will inform the investigators of such regulatory reports. Investigators must submit safety reports as required by their Institutional Review Board (IRB). Documentation of the submission to and receipt by the IRB should be retained for each IND safety report.

9.4 Assessment of Causal Relationship

A medically qualified investigator must assess the relationship of any adverse event to the use of the study drug, based on available information using the following guidelines:

1. Not related: There is not a reasonable causal relationship to the investigational product and the adverse event.

2. **Unlikely related**: No temporal association, or the cause of the event has been identified, or the drug or biologic cannot be implicated.

3. **Possibly related**: There is reasonable evidence to suggest a causal relationship between the drug and adverse event.

4. **Related**: There is evidence to suggest a causal relationship, and the influence of other factors is unlikely.

Relatedness to these complications will not be specifically assigned by the Data Monitoring Committee unless they are separately reported as suspected unexpected serious adverse reactions (SUSARs). **Expectedness**

The expectedness of an adverse event or suspected adverse reaction shall be assessed by a DCRI Safety Medical Monitor according to the package insert. Any AE that is not identified in nature, severity, or specificity in the current package insert is considered unexpected. Events that are not mentioned in the

package insert as occurring with a class of drugs or as anticipated from the pharmacological properties of the drug, but not specifically mentioned as occurring with the particular drug under investigation, are considered unexpected.

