9.6 Safety Monitoring

The data coordinating center (DCC) will monitor safety during the conduct of the study. The study sponsor will review all potential unexpected study drug related serious adverse events at the time of SAE notification by DCRI Safety Surveillance and confirm whether the event is a suspected unexpected serious adverse reaction (SUSAR). The data monitoring committee (DMC) will monitor safety every 6 months as per the DMC charter. Annual and expedited reports will be submitted to the FDA as required.

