11 DATA MANAGEMENT

11.1 Data entry

The majority of data for the STRESS trial will be captured via the STS-CHSD. Sites must enter the IBM Clinical Development subject ID into the participating subjects STS-CHSD record under the "STS-related clinical trial ID" tab/variable. This identifier must be entered into the STS database immediately after it is assigned. This identifier will be used to link the two databases. For other variables, the STS-CHSD includes specific data element definitions that must be closely followed (see section 11.2).

Serious, unexpected, study drug-related adverse events may require expedited reporting and therefore must be collected in an expedited fashion. Since the STS-CHSD data are only harvested every 6-months, a separate IBM Clinical Development database has been developed to capture these events. Study drug-related serious adverse events must be submitted into the IBM Clinical Development database within 1 business day of first becoming aware of the event. The IBM Clinical Development database will also be used to capture a select subset of additional variables including timing of medication administration, adverse events of interest that are felt to be study drug-related (see section 9.2) and timing of PK/PD/Biomarker sample collection (for participating sites).

In addition, a small subset of select post-operative laboratory administration variables (Table 4) need to be captured but are not incorporated into the STS-CHSD. These data must be collected from the electronic health record and the data entered directly into the IBM Clinical Development database.

As summarized above, the IBM Clinical Development subject ID will be used to link the two databases. As a safety control, sites will enter the STS "Operation ID" into the IBM Clinical Development database. In the event that the IBM Clinical Development subject ID is miss-entered into one of the databases, the STS Operation ID will be used to ensure accurate linkage.

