Clinical studies did not include sufficient numbers of subjects aged 65 and over to determine whether they respond differently from younger subjects. Other reported clinical experience has not identified differences in responses between the elderly and younger patients. In general, dose selection for an elderly patient should be cautious, usually starting at the low end of the dosing range, reflecting the greater frequency of decreased hepatic, renal, or cardiac function, and of concomitant disease or other drug therapy.

ADVERSE REACTIONS

The following adverse reactions have been reported with SOLU-MEDROL or other corticosteroids:

Allergic reactions: Allergic or hypersensitivity reactions, anaphylactoid reaction, anaphylaxis, angioedema.

Blood and lymphatic system disorders: Leukocytosis.

Cardiovascular: Bradycardia, cardiac arrest, cardiac arrhythmias, cardiac enlargement, circulatory collapse, congestive heart failure, fat embolism, hypertension, hypertrophic cardiomyopathy in premature infants, myocardial rupture following recent myocardial infarction (see **WARNINGS**), pulmonary edema, syncope, tachycardia, thromboembolism, thrombophlebitis, vasculitis.

Dermatologic: Acne, allergic dermatitis, burning or tingling (especially in the perineal area after intravenous injection), cutaneous and subcutaneous atrophy, dry scaly skin, ecchymoses and

Page 86 of 96

petechiae, edema, erythema, hyperpigmentation, hypopigmentation, impaired wound healing, increased sweating, rash, sterile abscess, striae, suppressed reactions to skin tests, thin fragile skin, thinning scalp hair, urticaria.

Endocrine: Decreased carbohydrate and glucose tolerance, development of cushingoid state, glycosuria, hirsutism, hypertrichosis, increased requirements for insulin or oral hypoglycemic agents in diabetes, manifestations of latent diabetes mellitus, menstrual irregularities, secondary adrenocortical and pituitary unresponsiveness (particularly in times of stress, as in trauma, surgery, or illness), suppression of growth in pediatric patients.

Fluid and electrolyte disturbances: Congestive heart failure in susceptible patients, fluid retention, hypokalemic alkalosis, potassium loss, sodium retention.

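### The second expectedness sentence in section 9.4 has a stray 'not', so events listed only as corticosteroid class effects are not classed as unexpected

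*Combined protocol and SAP*

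**What the plan says.** Section 9.4 (Expectedness) gives the assessment to a "Safety Medical Monitor according to the package insert". Two sentences then define the rule.

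- Sentence 1: "Any AE that is not identified in nature, severity, or specificity in the current package insert is considered unexpected".
- Sentence 2 opens "Events that are not mentioned in the", continues "package insert as occurring with a class of drugs or as anticipated from the pharmacological properties of the drug, but not specifically mentioned", and ends "as occurring with the particular drug under investigation, are considered unexpected".

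The reference document is Appendix B (section 15.3). Its Adverse Reactions section opens with one combined list: "The following adverse reactions have been reported with SOLU-MEDROL or other corticosteroids". The list does not separate reactions seen with the study drug from those seen with other members of the class.

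Other sections act on the result. Section 9.6 has the sponsor review potentially unexpected drug-related serious events and decide whether each is a SUSAR. Section 9.3 provides continuous monitoring for SUSARs, against a 6-monthly DMC review of registry events. Section 11.1 says: "Serious, unexpected, study drug-related adverse events may require expedited reporting".

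**The concern.** In sentence 2 the word *but* announces a contrast: mentioned for the class, yet not for this drug. The contrast needs a positive first half, and the printed first half is negative. The sentence therefore adds nothing to sentence 1, and the case it was evidently written to settle, an event known for the class but not for the drug, is left without a rule.

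The case can arise. The insert makes several statements at class level: cardiac free-wall rupture after recent infarction (Warnings, Cardio-renal), bowel perforation (Precautions, Gastrointestinal) and acute myopathy (Precautions, Neurologic-Psychiatric). Each is worded for steroids or corticosteroids in general. The pooled heading of the main list raises the same question for many more entries.

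At stake is whether a drug-related serious event of this kind is treated as a SUSAR. That status brings individual confirmation by the sponsor and continuous monitoring. Under section 9.4 it is also the condition on which the DMC assigns relatedness to a complication.

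**Working it through.** No arithmetic applies. The check is a logical one on the two sentences.

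Let C mean that the insert mentions the event as a class effect or as anticipated from the pharmacology, and D that the insert names it specifically for the study drug. Sentence 2 as printed calls an event unexpected when (not C) and (not D). With the first *not* removed, the condition becomes C and (not D).

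| C | D | Sentence 1 | Sentence 2 as printed | Sentence 2 without the first *not* |
|---|---|---|---|---|
| no | no | unexpected | unexpected (repeats sentence 1) | silent; sentence 1 decides |
| yes | no | silent if the event matches the listing | silent | unexpected |
| no | yes | silent if the event matches the listing | silent | silent |
| yes | yes | silent if the event matches the listing | silent | silent |

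Three results follow.

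1. As printed, sentence 2 acts only in the first row, where sentence 1 has already decided. It is redundant.
2. Deleting the word changes the overall classification in one row of four, the class-effect-only row, from not unexpected to unexpected.
3. If the slip were instead *but* for *or*, the condition would be (not C) or (not D). The class-only row would again be unexpected, so both repairs agree there. That alternative would also make an event named for the drug unexpected whenever it was not separately listed for the class, which makes little sense. Deletion is the cleaner repair.

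The table also shows what deletion does not settle. To use it, the monitor must know whether an entry is C only or also D. For the entries in the pooled list, the insert's heading does not say.

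**The case against.** The strongest reply is that the slip is real but little follows from it. Most of the particulars stand.

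- **No event is declared expected.** Sentence 2 only adds to the unexpected group. A reader might infer that every class effect on the label becomes expected and is barred from expediting. The text does not say so: sentence 1 still catches an event that differs from its listing in nature, severity or specificity. One could stretch *specificity* to cover all class-only listings, but a reporting rule should not depend on that reading when the next sentence was written to decide the matter.
- **Reporting by sites is unaffected.** Sections 6.4 and 9.1 require all serious drug-related events within 1 business day, whatever their expectedness. Section 9.3 leaves the expediting decision with the sponsor, and section 6.4 refers to possible expedited reporting without requiring that the event be unexpected.
- **Few events get this far.** Section 9.5 keeps events attributed to the heart disease or surgical recovery, including registry-listed complications, out of the drug-related serious-event database. A reader might take cardiac arrest, convulsions and thromboembolism as the events at risk. They are poor examples: cardiac arrest, seizure and several thrombosis terms are on the registry complication list in Appendix A1, and the insert's Dosage and Administration section ties cardiac arrest to SOLU-MEDROL itself. Intestinal perforation is a better example, since that list has no named item for it.
- **The DMC is not confined to 6-monthly meetings.** A reader might infer that such events otherwise wait half a year. The synopsis lets the DMC review data at any time, and section 9.7 notifies it once more than 3 subjects have active-drug-related serious events of the same Preferred Term. That trigger needs at least four cases, whereas SUSAR review works on one.
- **Prospective effect may be small.** Version 6.0 is dated March 2022, and the amendment table describes a study near its end, with serious drug-related events collected for only 7 days after dosing.

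These points limit the consequence. None of them makes the printed sentence do its work.

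**Conclusion.** The rule is wrong as written. Sentence 2 of the expectedness definition covers only events absent from the insert, and class-effect-only events fall outside it. Followed literally, a drug-related serious event of that kind that matches its listing could miss SUSAR confirmation under section 9.6 and continuous monitoring under section 9.3.

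The size is modest. No sample size, alpha, power or efficacy result is touched, and the documents do not allow a count of affected events. The conclusion rests on two assumptions: that the monitor applies the sentence as printed, and that a class-level listing counts as identifying the event under sentence 1.

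A reader might go further and hold that an entry found only in the pooled list can never make an event expected. No section states that, and it could turn much of the main adverse-reaction list into unexpected events. The pooled heading leaves a question open; it does not supply the answer.

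**What to change.** Delete the word *not* from the opening "Events that are not mentioned in the" in section 9.4 and leave the rest of the sentence as it stands. It will then class as unexpected those events the insert mentions for the class, or as anticipated from the pharmacology, but not for this drug.

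Add one sentence saying how entries in the pooled Adverse Reactions list of Appendix B are to be classified, so that two monitors would reach the same answer. What that classification should be is for the sponsor to decide.

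The cost is a one-word deletion, one added sentence and possibly a few more expedited reports. Site procedures and data collection do not change.
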